#### **Methods and Procedures**

The trial is designed to prove the efficacy and safety of the invisa-RED Technology Elite Low-level Laser Therapy (LLLT) device. The trial will compare results between two groups; the first will be treated using a fully functional invisa-RED Technology Elite device; this group will be internally designated the Usual Care Group. The second, a control group, will be treated utilizing a nonfunctional invisa-RED Technology Elite device; this group will be referred to internally as the Sham Group.

The sham device will consist of an invisa-RED Technology Elite device that will appear to operate as the Usual Care Group device to the operator, but the laser diodes will be disabled and will receive no power. If staff or a participant questions the efficacy of the sham device, an assertion may be made that only a near infrared, nonvisible frequency of light, is being employed.

The trial will be conducted employing a double blind study methodology; participants will be randomly assigned to each group through a drawing, neither participants nor clinicians will know to which trial group they are assigned. To ensure the double blind; treatment for the two groups will occur on separate days of the week. All participants will receive therapy at the [name] Chiropractic Center located in Hixson, TN. Group 1 will be assigned Monday, Wednesday, Friday, and Group 2; Tuesday, Thursday, and Saturday. Additionally staff administering the trial therapy will be assigned to work with one (1) group exclusively.

A simplified weight loss protocol will be employed based on the "Consultation Protocol" from the invisa-Red Training Manual. All study participants will undergo nine (9) therapy sessions of 20 minutes each; using a singular protocol setting for pulse (3.5s) and delay (0.2s), but power settings will be based on the participants Fitzpatrick Scale skin type. For skin types i and ii a power setting of 7 will be used, for skin types iii and iv a power setting of 6, for skin types v and vi a power setting of 4 will be employed. At the conclusion of the nine (9) therapy sessions; the change in body fat percentage, weight, and inches lost of the two groups will be statistically analyzed to determine the efficacy of the invisa-RED Technology Elite as a weight loss therapy. Any medical errors will be included in the statistical analysis.

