#### **Staff Training and Certification**

All staff involved in conducting the clinical trial will undergo training and be certified on the use, safety, and clinical procedures of the invisa-RED Technology Elite.

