The invisa-RED Elite device employs Class 3b laser diodes in a system of "paddles" each containing multiple diodes. Class 3B lasers are hazardous for eye exposure; therefore during therapy protective eyewear is recommended for staff, the individual undergoing treatment, and any others in the room. Eye safety is further enhanced by standard invisa-RED Elite clinical procedures, which are designed to eliminate exposure of the eyes of the patient and proximate individuals to direct laser light. These clinical procedures dictate that the paddles are to be 1) placed on the area to be treated, 2) secured if required, and then and only then 3) the system is activated and treatment begun. This eliminates the chance of any direct laser light entering the eye.

Class 3B lasers can heat skin and materials but are not considered a burn hazard. However treatment protocol standards found in the users manual do recommend power settings, pulse and delay be adjusted for the patients Fitzpatrick Scale skin type; as differing skin tones result in a variable coefficient of absorption of electromagnetic energy. If these recommendations are not followed, the therapy may result in mild sunburn like effect and or skin sensitivity. Additionally each patient is asked to verbally attest to his or her comfort level at the start of each therapy session and further instructed to notify staff of any discomfort at any time. As stated in the user manual and stressed during invisa-RED Elite device Training and Certification the following contraindications and precautions for patients will apply:

- If you are pregnant, trying to get pregnant or nursing laser light therapy should be received only after the end of these conditions. There is no evidence of harm to a an unborn baby however there have been no safety tests either, so for medical legal reasons we recommend never treating areas directly over a developing child.
- Individuals with hypertension, light sensitive epilepsy, cancer, heart disease, infectious skin disease, and severe varicose veins should not use this device.
- People suffering from infectious and acute disease such as a fever should not use this device.
- People who have hemorrhagic disease, vascular ruptures, skin inflammation, or any disease of the skin should not use this device.
- People who have immune system dysfunction such as Leukemia, Hemophilia, etc., and light sensitive persons should not use this device.

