Statistical Analysis Plan

Cover Page

for the Clinical Study

"Comparing the Efficacy of a Dual-Frequency Laser-Emitting Device, the "invisared-RED Elite", With a Sham Device as Therapy for the Loss of Adipose Tissue (Body Fat) and Aesthetics in Overweight Individuals"

NCT03811093

May 7, 2019

Statistical Analysis Plan

for

Invisa-RED Clinical Trial

Research Questions:

Research Question One (1): Is there a statistically significant difference in Percentage of Body Fat Lost when using an invisa-RED Technology Elite Low-level Laser Therapy (LLLT) device when compared with a sham (placebo) device in an approved and standardized clinical protocol?

Null Hypothesis One (1): There is not a statistically significant difference in Percentage of Body Fat Lost when using an invisa-RED Technology Elite Low-level Laser Therapy (LLLT) device when compared with a sham (placebo) device as a therapy in an approved and standardized clinical protocol.

Alternative Hypothesis One (1): There is a statistically significant difference in Percentage of Body Fat Lost when using an invisa-RED Technology Elite Low-level Laser Therapy (LLLT) device when compared with a sham (placebo) device as a therapy in an approved and standardized clinical protocol.

Research Question Two (2): Is there a statistically significant difference in Inches Lost when using an invisa-RED Technology Elite Low-level Laser Therapy (LLLT) device when compared with a sham (placebo) device in an approved and standardized clinical protocol?

Null Hypothesis Two (2): There is not a statistically significant difference in Inches Lost when using an invisa-RED Technology Elite Low-level Laser Therapy (LLLT) device when compared with a sham (placebo) device in an approved and standardized clinical protocol.

Alternative Hypothesis Two (2): There is a statistically significant difference in Inches Lost when using an invisa-RED Technology Elite Low-level Laser Therapy (LLLT) device when compared with a sham (placebo) device in an approved and standardized clinical protocol.

Research Question Three(3): Is there a statistically significant difference in Pounds of Body Fat Lost when using an invisa-RED Technology Elite Low-level Laser Therapy (LLLT) device as a therapy when compared with a sham (placebo) device in an approved and standardized clinical protocol?

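### The cover answer reserved for questions about the sham can reveal the arm and undermines the stated double blind; one identical statement in both arms would remove that cue.

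*Protocol*

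**What the plan says.** Four statements in the Protocol's Methods and Procedures bear on this point.

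- **The sham.** It is the same model of device, meant to look to the operator as though it is working, but "the laser diodes will be disabled and will receive no power".
- **The cover answer.** "If staff or a participant questions the efficacy of the sham device", then "an assertion may be made that only a near infrared, nonvisible frequency of light, is being employed". The section does not say who gives this answer, and it provides none for questions about the active device.
- **The blind.** The trial is called double blind: "neither participants nor clinicians will know to which trial group they are assigned". The SAP's Analysis section repeats the double-blind description.
- **The logistics.** One group attends Monday, Wednesday and Friday, the other Tuesday, Thursday and Saturday. Each staff member giving therapy works with one group only.

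Two statements elsewhere matter. Staff Training and Certification says: "All staff involved in conducting the clinical trial will undergo training and be certified on the use", and goes on to safety and clinical procedures. The SAP title begins: "Comparing the Efficacy of a Dual-Frequency Laser-Emitting Device".

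**The concern.** A blind depends on both arms hearing and seeing the same things. Here the plan itself supplies something that belongs to one arm only. To apply the rule as written, the speaker has to know that the device in question is the sham. A listener who knows the rule, or who knows that the description does not fit the device, can work out the arm.

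If the arm becomes known, the difference between groups may reflect expectation as well as the device. Expectation could act through what participants do outside the sessions or through how the outcomes are measured. The documents do not fix diet or exercise during the trial, do not say how inches are measured, and do not say whether the measurer is blinded. Nor do they plan a record of when the answer is used, or any question on which arm people believe they are in. A leak would pass unnoticed.

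**Working it through.** The plan gives no figure to reproduce on this point. The main check sets the statements side by side; a short calculation then shows what an assumed bias would do.

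**1. Who can give the answer?** The trigger is a doubt about the sham device. Someone following the rule must know that the device is the sham. The same section says clinicians do not know the assignment and names no unblinded person to answer in their place. Either a blinded person is being asked to do something that needs the code, or an unblinded role exists and is not described.

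**2. Does the answer fit the device?** It says that a single near-infrared frequency is in use. The SAP title says dual-frequency, so the answer does not match the working device as titled. It is also untrue of the sham, whose diodes are unpowered. The Protocol gives no wavelengths and does not say whether the active light is visible, so the conflict with the working device rests on the SAP title alone.

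**3. Who could recognise it as sham-specific?**
- The person giving it: yes, if the rule is followed as written.
- Staff who have been trained on the device: possibly, if they know that it is dual-frequency or know the rule.
- A participant who knows neither the rule nor the device specification: not necessarily.

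**4. How far would one inference spread?** Weekdays and staff are both fixed by group. Identifying the arm of one participant identifies everyone treated on those days by those staff, which is about 20 people if the 40 are split equally.

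**5. Illustration of size.** Inputs: 40 participants (Protocol, Criteria for Participants), taken as 20 per arm; two-sided t-test at 0.05 (SAP, Analysis); no true device effect; a shift of d standard deviations in one arm's mean, which is an assumption. Degrees of freedom are 20 + 20 − 2 = 38 and the critical value is 2.024. The noncentrality is d × √(20/2) = 3.162 d. The rejection probability is P(|T| > 2.024) for a noncentral t.

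| Assumed shift d (SD) | Noncentrality | Rejection probability, per outcome |
|---|---|---|
| 0 | 0 | 0.050 |
| 0.2 | 0.632 | 0.095 (9.46%) |
| 0.3 | 0.949 | 0.152 |
| 0.5 | 1.581 | 0.338 |

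These figures would be the same for any bias of that size, whatever its source. They also assume that the whole arm's mean moves, whereas the cover answer is used only when someone asks.

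**The case against.** The strongest reply is that the answer exists to protect the blind. It is permitted, not required, and it is meant to reassure someone who has begun to doubt. A reader might infer from the text that using it reveals the arm and breaks the blind. The documents do not support that. Nothing says participants are told that the answer is sham-only or that the device has two frequencies, so a participant could hear it and learn nothing. An unblinded person who neither treats nor measures could also give it without contradicting the sentence on blinding; the text simply does not describe one. This stands, and it is why the point is that the answer *can* reveal the arm.

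The conflict with the device description rests on one term in the SAP title, and the training section does not mention frequencies. That trained staff *would* notice is therefore an inference; that they *could* is reasonable.

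A reader might also argue that sham participants are bound to ask because they feel no warmth. The Protocol's Risk/Benefit Assessment does say "Class 3B lasers can heat skin and materials", but the sentence continues that these lasers are not considered a burn hazard. It describes a laser class, and nothing says that warmth is felt at the trial's settings. The argument should not be used.

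Finally, it is tempting to require an arm guess after the ninth session and to allow the term double blind only if guesses are near chance. By then people who have lost inches will tend to guess active, so an effective device could fail the test with the blind intact. The sample is also too small: 10 correct out of 20 has an exact 95% interval of about 27% to 73%.

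What the reply does not answer is that the cue is specific to one arm, that the plan creates it, and that the blind does not need it.

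**Conclusion.** The concern holds as a risk that the plan creates for itself. A reply reserved for the sham requires arm knowledge that the same section says clinicians lack, and its content conflicts with the SAP title and with the unpowered diodes. It can reveal the arm, most plausibly to the person giving it and to trained staff, and so it undermines the stated double blind. The separation of groups by weekday and by staff means that one inference could expose a whole group.

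The size of any bias is unknown. The rates of about 9%, 15% and 34% illustrate assumed shifts of 0.2, 0.3 and 0.5 SD with 20 per arm; they do not estimate what this wording would cause. A reader should not infer that the trial's false-positive rate is 34%, because the documents give no estimate of the shift. The conclusion rests on the rule being followed as written and on the SAP title describing the device correctly.

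**What to change.** 1. In the Protocol, Methods and Procedures, delete the sham-only answer. Replace it with one neutral statement given in identical words to every participant and every operator in both arms before the first session, and repeated unchanged if anyone asks later. It should be true of both devices, for example that light may or may not be noticed. Nobody then needs to know the arm in order to answer.
2. Reconcile the Protocol's near-infrared wording with the dual-frequency description in the SAP title.
3. Optionally, ask each participant early in treatment, before results are apparent, which device they believe they are receiving. Report the guesses descriptively by arm, with no pass/fail rule for the term double blind.

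The cost is one script and, if step 3 is used, one question per person. The device, the settings and the schedule are untouched. The fix has limits: any cue from the sham's lack of light would remain, and so would the separation of arms by day and staff, which is a separate weakness.

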## **Criteria for Participants**

The number of participants is projected to be forty (40).

There will be an equitable distribution of male and female participants.

Women who are pregnant, trying to get pregnant, or nursing will be excluded from the study, as they should not receive Low-level Laser Therapy (LLLT). There is no evidence of harm to a an unborn baby however there have been no safety tests either, so for medical legal reasons we recommend never treating such individuals.

The participants will be between the ages of 18-65 years.

The ethnicity of the participants will be equitably distributed.

Inclusion criteria will be individuals that may benefit from a weight loss therapy.

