#### Subject Identification, Recruitment And Consent/Assent

At roadway intersections in close proximity to the [name] Chiropractic Clinic signage will be erected containing the verbiage: "Weight Loss Clinical Study, 40 Participants, [contact]" in order to recruit study volunteers from the community.

The clinic's patients will be provided an opportunity to volunteer for consideration as a trial participant.

The primary investigator will conduct all subject interviews and obtain informed consent. A thorough disclosure of all clinical process, contraindications, and any risk will be discussed with candidates for the trial.

All candidates will be older than the age of majority in the state of Tennessee (18 years old) but none shall be older than 65 years of age.

No candidates of diminished capacity will be considered for inclusion in the trial.

Capacity is a functional assessment and a clinical determination about a specific decision that can be made by any clinician familiar with a patient's case. The four key components addressed during the candidates capacity evaluation include: 1) communicating a choice, 2) understanding, 3) appreciation, and 4) rationalization/reasoning.

There shall be no cost incurred by candidates for inclusion in the study or individuals selected to participate in the study.

No monetary remuneration will be offered participants in the study. However an offer will be made "post blind" to the participants who received treatment using the sham device for an additional nine (9) sessions of treatments using a fully functional invisa-RED Technology Elite device. This offer will provide the participants treated with the sham device the opportunity to benefit from the weight loss and aesthetics therapy.

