Null Hypothesis Three (3): There is not a statistically significant difference in Pounds of Body Fat Lost when using an invisa-RED Technology Elite Low-level Laser Therapy (LLLT) device when compared with a sham (placebo) device as a therapy in an approved and standardized clinical protocol.

Alternative Hypothesis Three (3): There is a statistically significant difference in Pounds of Body Fat Lost when using an invisa-RED Technology Elite Low-level Laser Therapy (LLLT) device when compared with a sham (placebo) device as a therapy in an approved and standardized clinical protocol.

Data Sets/Populations:

Criteria for Participants:

Participants will be taken from a random population of respondents to both email and social media recruitment. The number of participants is projected to be forty (40). There will be an equitable distribution of male and female participants. Women who are pregnant, trying to get pregnant, or nursing will be excluded from the study, as they should not receive Low-level Laser Therapy (LLLT). Note; there is no evidence of harm to an unborn baby however there have been no safety tests either, so for medical legal reasons we recommend never treating such individuals. The participants will be between the ages of 18-75 years. Inclusion criteria will be individuals that may benefit from a weight loss therapy.

Exclusion criteria will include the following:

- If you are pregnant, trying to get pregnant or nursing laser light therapy should be received only after the end of these conditions. There is no evidence of harm to an unborn baby however there have been no safety tests either, so for medical legal reasons we recommend never treating areas directly over a developing child.
- Individuals with hypertension, light sensitive epilepsy, cancer, heart disease, infectious skin disease, and severe varicose veins should not use this device.
- People suffering from infectious and acute disease such as a fever should not use this device.
- People who have hemorrhagic disease, vascular ruptures, skin inflammation, or any disease of the skin should not use this device.
- People who have immune system dysfunction such as Leukemia, Hemophilia, etc., and light sensitive persons should not use this device.
- Individuals with a history of melanoma, raised moles, suspicious lesions, keloid scar formation, or healing problems should not undergo laser light therapy.

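### The timing and concealment of the drawing are not described, and sex is neither stratified in the allocation nor used in the analysis

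*Protocol*

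**What the plan says.** - **Method.** Protocol, Methods and Procedures: "participants will be randomly assigned to each group through a drawing". The same sentence promises that "neither participants nor clinicians will know to which trial group they are assigned". The SAP (end of Data Sets/Populations) says only that assignment is random.
- **Schedule.** Same protocol section: "Group 1 will be assigned Monday, Wednesday, Friday, and Group 2; Tuesday, Thursday, and Saturday". Each member of the treating staff works with one group only.
- **Who recruits.** Protocol, Subject Identification, Recruitment And Consent/Assent: "The primary investigator will conduct all subject interviews and obtain informed consent". The clinic's own patients may volunteer.
- **Who may enter.** Protocol, Criteria for Participants, apart from an age range: "Inclusion criteria will be individuals that may benefit from a weight loss therapy". A list of exclusions follows, and candidates are vetted against the device's indications and contraindications.
- **Order.** The SAP (end of Data Sets/Populations) has people screened and selected first; the roughly 40 who are selected are then randomised.
- **Balance.** SAP, Criteria for Participants: "There will be an equitable distribution of male and female participants". The protocol says the same and adds: "The ethnicity of the participants will be equitably distributed". Both statements concern the participants as a whole.
- **Analysis.** SAP, Analysis: three independent-samples t-tests, two-sided at 0.05, with no covariate or stratification factor.

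Neither document gives the allocation ratio, who draws, from what, whether slips are replaced, whether draws are logged, or whether a redraw or swap is allowed.

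**The concern.** Concealment and blinding protect against different things. Blinding keeps people from knowing the treatment after assignment. Concealment keeps the person who admits participants from foreseeing the next assignment. The protocol promises the first and does not mention the second.

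The gap matters here for three reasons. One person conducts every interview and obtains every consent. The inclusion criterion has no BMI or body-fat threshold, so it leaves room for judgement. The weekday schedule makes group membership visible to anyone who sees the appointment book. If that person could foresee assignments and knew or suspected which group had the working device, the choice of whom to admit could differ by arm. No later t-test repairs that.

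The sex question is separate and smaller. Both documents treat the mix of men and women as worth controlling, but neither applies it to the arms or to the analysis, which is where it would help the comparison.

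**Working it through.** The plan has no figure of its own to reproduce: 40 is a projection without a derivation.

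**1. When could eligibility respond to allocation?**

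The SAP fixes the order for each person: selection, then assignment. It does not fix the order for the trial as a whole. Two readings fit the text.

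- All 40 are selected, then one drawing is held. Nothing can be foreseen, and the problem does not arise.
- People are selected and drawn one after another. Someone screened 25th is judged after 24 assignments have shown themselves through the weekdays.

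**2. How foreseeable would assignments be under rolling enrolment?**

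Assumptions: 20 slips per arm, drawn one at a time without replacement, with all past draws known. Guessing the group with more slips left gives an expected number correct of

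n + 4^n / (2 × C(2n, n)) − 1/2, with n = 20.

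- 4^20 = 1,099,511,627,776 and C(40, 20) = 137,846,528,820
- 4^20 / (2 × C(40, 20)) = 3.988
- 20 + 3.988 − 0.5 = **23.49 of 40** (59%), against 20 (50%) by chance

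On average the last 2 × 20/21 = 1.9 assignments are certain. If each draw were independent, such as a coin toss, the figure would be 20 of 40. The range across the unstated mechanisms considered here is therefore 20 to 23.5.

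**3. How often would a draw that ignores sex split men unevenly?**

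Assumptions: 20 men, 20 women, exactly 20 per arm. The number of men in one arm is hypergeometric: P(k) = C(20, k)² / C(40, 20).

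| Men, arm against arm | Probability |
|---|---|
| 10:10 | 0.248 |
| 11:9 either way | 0.409 |
| 12:8 or worse | 1 − 0.248 − 0.409 = **0.343** |
| 13:7 or worse | **0.113** |
| 14:6 or worse | 0.026 |

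With independent draws instead, the share of men differs between arms by 20 percentage points or more 26.8% of the time, and by 30 points or more 8.1%. The arms then come out at exactly 20 and 20 only 12.5% of the time.

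**4. What does an uneven split do to the result?**

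The documents give no sex effect; assume 0.3 to 1.0 SD (within-sex SD). The shift in the arm difference is the difference in the share of men times the sex effect.

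- 12:8: share difference 0.60 − 0.40 = 0.2, so the shift is 0.06 to 0.20 SD
- 13:7: share difference 0.65 − 0.35 = 0.3, so the shift is 0.09 to 0.30 SD

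The standard error of the difference at 20 per arm is √(2/20) = 0.32 SD. These shifts fall in either direction with equal chance, so they add noise and not bias.

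**5. What would using sex gain?**

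With half men, ignoring sex multiplies the variance by 1 + d²/4, where d is the sex effect in SD. Taking sex into account shrinks the standard error by 1 − 1/√(1 + d²/4): 1.1% at d = 0.3 and 10.6% at d = 1.0.

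**The case against.** A reader might infer that the draw is open, that eligibility is settled after allocation, and that a promise of balance has been broken. The documents support none of these.

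- **Silence is not an open draw.** The documents do not describe concealment; they do not describe its absence either. Nor do they say that draws go unrecorded, and running two weekday schedules needs some record of who is in which group. This stands.
- **Selection comes first.** The SAP says so for each person. This rules out deciding eligibility after that person's own draw. It does not rule out foreseeing the next one under rolling enrolment.
- **A guessed group is not a guessed device.** If slips say only Group 1 or Group 2 and the key is withheld, counting slips gives no direction in which to steer. This stands as a condition on the concern. Its force is limited because everyone in a group shares weekdays and device status, so identifying one person's device identifies the whole group's. Methods and Procedures itself expects that staff or participants may question the sham.
- **Eligibility is not judgement alone.** The exclusions are many and mostly specific, and written guidelines apply. That narrows the discretion without removing it.
- **Balance within arms was never promised.** True. Chance imbalance is also already allowed for in the t-test's error rate, so calling it confounding that biases the test would be wrong.

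**Conclusion.** The concern holds in a conditional form. The mechanism, timing and concealment of the drawing are not described, and nothing requires one draw from a closed list. If enrolment is rolling and past assignments can be read from the weekdays, up to 23.5 of 40 assignments can be guessed, against 20 by chance. That figure rests on fixed 20/20 slips drawn without replacement. It becomes a route to bias only if the device behind a group is also known or suspected. The resulting bias cannot be sized from the documents.

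The sex point is a matter of precision. Under the assumed 20 men, 20 women and 20 per arm, a 12:8 or worse split occurs 34% of the time and 13:7 or worse 11%. The test remains valid. The gain from using sex is modest unless men and women differ strongly in what they lose.

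The change is worth making before enrolment starts: it is cheap, and without it a reader cannot confirm that the allocation was protected.

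**What to change.** In Methods and Procedures, replace the drawing with wording to this effect:

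> An existing team member who does not interview, treat or measure participants generates and holds a computer-made 1:1 allocation list, stratified by sex. Assignments are released either in one step after the list of eligible, consented people is closed, or one at a time from sequentially numbered, opaque, sealed envelopes (random block sizes), each opened only after eligibility and consent are signed. Every assignment is logged with its date. Redraws and swaps are not allowed.

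The one-step release is preferable if all 40 can be enrolled before treatment starts, because the weekdays reveal past assignments and small blocks are then easier to guess than a single 20/20 draw. With a known block size of 4, the formula above with n = 2 gives 2 + 16/12 − 0.5 = 2.83 correct per block, or 28.3 of 40 over ten blocks. Varying the block size and not disclosing it reduces this but does not remove it.

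In the SAP, Analysis, replace each t-test by a linear model with group and sex as factors. Stratifying without this leaves the variation between men and women in the error term and forgoes the gain.

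Cost: a little preparation, one paragraph in the protocol, one sentence in the SAP, and one residual degree of freedom (37 in place of 38 with 40 people). The list holder must stay out of recruitment, treatment and measurement. With 20 men and 20 women and complete blocks of 4, the split becomes 10:10 in each sex; an incomplete last block leaves at most a difference of 2 people within a sex.
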